**Phase two:**

Study candidates will randomly be assigned (20 per group) to practice for 15minutes/day their intubations skills with the iLarynx application downloaded to their smart phones or Ipads. The other group (20candidates) will be asked not to practice their intubation skills. At the end of one week both groups will be retested on a mannequin by the same blinded examiner to obtain a new learning curve, global assessment score and checklist. Both orientations of the mannequin will be tested and the order randomly assigned.

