**Research Aims:**

1. **Research Questions(s)** (1) Does spatial orientation of a novice in relation to a mannequin (supine vs upright) impact on the development of fiberoptic intubation skills (2) Is it necessary to teach both orientations or is the supine view transferable to the upright position. (3) Which method demonstrates longer skill retention.
  
2. **Hypotheses** (1) Both orientations must be practiced. (2) The upright skill is harder to learn but is retained for longer.

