**Significance:**

Novices better prepared in the skills of manipulating a fiberoptic will take less time and have a higher success rate of fiberoptic intubation. These skills must be taught for both spatial orientations and practiced to be retained

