**Statistical Methods:**

60 medical students will be consented to allow for dropout. Based on a repeated – measures design with one between-factor design (supine vs upright) and one within factor (repetitions), four groups with 10 subjects each with each subject measured 10 times, achieves 87% power to measure a difference in time to visualize the carina using a Geisser -Greenhouse Corrected F-test at a 5% significance level assuming an effect size of 0.7. Groups A ,B,C,D will be compared. The two outcome measures global rating scale (GRS) and examiner check list (ECL) scores will be analyzed using a two-way, mixed design ANOVA. Categorical data such as success failure will be analyzed by Fisher exact test. Time to intubation will be analyzed using the MannWhitney U test.

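### The randomised practice comparison in Phase two has no named analysis and makes no use of the Phase one scores; adjusting for them would gain precision at little cost

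*Combined protocol and SAP*

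**What the plan says.** All references are to the combined protocol and SAP.

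- **Phase two** sets up a randomised 1:1 comparison: "Study candidates will randomly be assigned (20 per group) to practice for 15minutes/day their intubations skills with the iLarynx application". For the comparator, "The other group (20candidates) will be asked not to practice their intubation skills". Both arms are retested after a week on the same kinds of measure.
- **Phase one** has a blinded examiner record learning curves, a global rating scale (GRS) and a checklist for every student, on the mannequin in both orientations. The order of the phases and the Phase one table place these scores before the practice week. Phase two does not say when its allocation is made.
- **Significance** draws a conclusion that depends on this comparison: "These skills must be taught for both spatial orientations and practiced to be retained".
- **Statistical Methods** give, in the power sentence, "one between-factor design (supine vs upright) and one within factor (repetitions", and then state "Groups A ,B,C,D will be compared". GRS and checklist scores get a two-way mixed ANOVA whose factors are not named. Success or failure gets Fisher's exact test. For time, "Time to intubation will be analyzed using the MannWhitney U test". Practice is not mentioned and no covariate appears.
- **Research Aims** ask "Which method demonstrates longer skill retention" and hypothesise "The upright skill is harder to learn but is retained for longer". Retention is not defined as a measure.

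**The concern.** A randomised comparison that supports a stated conclusion has no analysis assigned to it. Each student is due to have been measured on the same task before the practice week, and that measurement is probably the best available predictor of the retest score. None of the stated methods uses it as a covariate, and the Mann-Whitney test for time to intubation cannot. With 20 students per arm, avoidable between-student variation matters.

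A second, smaller issue concerns research question 3. The plan itself expects the upright skill to be harder to learn, so students taught in the two orientations may finish Phase one at different levels. A difference between them at one week is a valid statement about one-week performance. It does not by itself show that one skill was better retained.

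**Working it through.** **The plan's own power figure.** The stated 87% (four groups of 10, 10 measurements each, 5% level, effect size 0.7) can be neither confirmed nor refuted, because the type of effect size, the correlation and the sphericity correction are not given. Read as Cohen's f at student level, 0.7 gives 95.4% for four groups of 10 and 84.1% for 10 vs 10. A repetition main effect with noncentrality 40 × 0.7² = 19.6 gives 88.6% without correction, but that does not compare groups. None of these readings powers the practice comparison.

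**Inputs.** From the documents: 20 per arm, two-sided 5%, 10 measurements per student. Assumed:
- a practice effect of 0.7 SD (the plan's number, read as a mean difference in SDs);
- a correlation r between Phase one and one-week scores of 0.3 to 0.7;
- a correlation ρ between attempts by the same student of 0.3 to 0.7;
- 10 attempts per session (the plan does not say whether the 10 are per session);
- approximately normal scores, such as log time.

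**Formulas.** Power comes from the noncentral t with noncentrality δ√(20/2).
- One-week score alone: δ = d, 38 df.
- ANCOVA on the Phase one score: δ = d/√(1 − r²), 37 df; with Group A–D added, 34 df.
- Change score: δ = d/√(2(1 − r)), 38 df.
- Mean of 10 attempts: d = 0.7/√(ρ + (1 − ρ)/10).

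**Ten attempts averaged.** The effect d in session-mean SDs is 1.151, 0.944 or 0.819 at ρ = 0.3, 0.5 or 0.7.

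| ρ | Unadjusted | ANCOVA r = 0.3 | r = 0.5 | r = 0.6 | r = 0.7 |
|---|---|---|---|---|---|
| 0.3 | 94% | 96% | 98% | 99% | >99% |
| 0.5 | 83% | 86% | 92% | 95% | 98% |
| 0.7 | 71% | 75% | 83% | 88% | 94% |

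At ρ = 0.5 the gain is 3 to 15 percentage points.

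**One score per session (d = 0.7).**

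| Analysis | r = 0.3 | r = 0.5 | r = 0.6 | r = 0.7 |
|---|---|---|---|---|
| One-week score, t-test | 58% | 58% | 58% | 58% |
| ANCOVA (37 df) | 62% | 70% | 77% | 86% |
| Change score | 45% | 58% | 67% | 80% |

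Mann-Whitney on the one-week score simulates at about 55–56%. For example, at r = 0.5, δ = 0.7/√0.75 = 0.808, and power is 70.2% (70.0% with Group A–D in the model). At r = 0, ANCOVA gives 57.8%, the same as unadjusted to one decimal, and 57.6% with Group A–D.

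**Why ANCOVA rather than practice × session.** With two sessions, a practice × session term in a mixed ANOVA is a test of change. The variance under ANCOVA relative to change is (1 − r²)/(2(1 − r)) = (1 + r)/2, which is below 1 for every r below 1.

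**Failed attempts.** A failed attempt has no intubation time. Simulations used one score per session, 0.7 SD, an assumed 20% failing at Phase one and among unpractised students at retest, and r from 0.3 to 0.7. Mann-Whitney with failures ranked last had about 55% power. Log-time ANCOVA had roughly 34–64% when failures were dropped and 58–82% when they were set at a time limit. The gain therefore depends on how failures are scored.

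**The case against.** The strongest reply is that this is an efficiency preference. Randomisation already makes the practice comparison fair, the documents give no correlation, and at r = 0.3 the gain is only 3 or 4 points in the main scenarios. That stands, and it limits the point to a cheap improvement.

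Three further replies also stand in part.
- The 58% to 86% range assumes one score per session, whereas the plan measures each student 10 times. The averaged-attempts figures are closer to the plan, and there the unadjusted analysis is already stronger.
- The mixed ANOVA for GRS and checklist has unnamed factors and could carry practice × session, so its ANOVA could draw on Phase one data. It would do so as a change score, which is less efficient than ANCOVA. Mann-Whitney could likewise be run on change, but the plan does not say so. Mann-Whitney is assigned only to time to intubation; time to visualise the carina is powered on a repeated-measures F-test.
- Replacing Mann-Whitney with log-time ANCOVA could lose power if failed attempts were dropped. The remedy needs a failure rule.

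A reader might infer that the practice comparison is biased or cannot be analysed as designed. The documents do not support this: allocation is random, the retest examiner is described as blinded, and a simple comparison of one-week scores would be valid.

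**Conclusion.** The point holds as a matter of precision. The randomised practice comparison is not named in the Statistical Methods, and no stated method adjusts for a Phase one score that is already collected. The gain is 3 to 15 points of power if ten attempts are averaged at ρ = 0.5 (from 83%), or 4 to 28 points with one score per session (from 58%), for r from 0.3 to 0.7. These sizes rest on assumed correlations and on reading 0.7 as a difference in SDs. The direction is safer: ANCOVA loses nothing material even at r = 0, provided failed attempts are kept. That the scores precede allocation is inferred from the phase order and table; they precede the practice week in any case.

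On research question 3, it would be tempting to say that the plan's retention comparison is wrong. The documents support less: retention is undefined, and a one-week difference between taught orientations should not alone be called a retention difference. Nor is ANCOVA on the Phase one score the clean answer there, because that score is taken after the randomised teaching and may be affected by it.

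**What to change.** 1. **Name the comparison.** Analyse one-week performance, practice vs no practice, by ANCOVA or a mixed model over attempts. Use the end-of-Phase-one score in the same mannequin orientation as covariate and Group A–D as a factor. State which attempts form each score.
2. **Score failures in advance.** For time, say how a failed attempt enters the analysis, for example set at a time limit, or ranked last with a rank ANCOVA. Do not drop failures.
3. **GRS and checklist.** Use the same adjusted analysis. If the mixed ANOVA is kept, name its factors and note that practice × session tests change, with less power.
4. **Question 3.** Report change since Phase one alongside one-week performance by taught orientation, and limit the retention claim to one week.

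The cost is SAP wording, 1 df for the covariate, 3 df for Group A–D, and the failure rule. No extra students, visits or measurements are needed. The change analysis in item 4 has less power than the one-week score when r is below 0.5, which is one reason to report both.

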**Phase one :**

Sixty medical students, novices in fiberoptic intubation use will be recruited and randomly assigned into one of two groups:

**Group A** (supine-supine) will first practice fiberoptic intubation with the iLarynx oriented in the supine position. Learning curves, global rating scale and checklist will then be obtained by a blinded examiner with the medical student using a real fiberoptic on a mannequin oriented in the supine, then upright position. At the end of one week, the same medical student will then perform the intubation with the mannequin in both positions.

**Group B** (upright-upright) will first practice fiberoptic intubation with the iLarynx oriented in the upright position. Learning curves, global assessment score and checklist will then be obtained by a blinded examiner with the medical student using a real fiberoptic on a mannequin oriented in the upright then supine position. At the end of one week, the same medical student will then perform the intubation with the mannequin in both positions.

**Group C** (supine –upright) will first practice fiberoptic intubation with the iLarynx oriented in the supine position. Learning curves, global assessment score and checklist will then be obtained by a blinded examiner with the medical student using a real fiberoptic on a mannequin oriented in the upright then supine position. At the end of one week, The same medical student will then perform the intubation with the mannequin in both positions.

**Group D** ( upright – supine) will first practice fiberoptic intubation with the iLarynx oriented in the upright position. Learning curves, global assessment score and checklist will then be obtained by a blinded examiner with the medical student using a real fiberoptic on a mannequin oriented in the supine, then upright position. At the

end of one week, the same medical student will then perform the intubation with the mannequin in both positions.

	teachin g		testing	testing		week	testing	testing
A	supine		supine	upright	i/droid	upright	supine	
B	upright		upright	supine	i/droid	supine	upright	
C	supine		upright	supine	i/droid	upright	supine	
D	upright		supine	upright	i/droid	upright	supine	

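### The practice randomisation in Phase two is not tied to Groups A–D and has no term in the planned analysis, although both act on the same one-week retest

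*Combined protocol and SAP*

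**What the plan says.** **Phase one.** The plan states: "Sixty medical students, novices in fiberoptic intubation use will be recruited and randomly assigned". Four groups, A to D, are then described. They differ in the iLarynx orientation used for teaching (supine in A and C, upright in B and D) and in the order of the first mannequin tests. For every group, the same student is tested again at one week in both positions.

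**Phase two.** The plan states: "Study candidates will randomly be assigned (20 per group) to practice for 15minutes/day their intubations skills". It continues: "The other group (20candidates) will be asked not to practice their intubation skills". Both groups are retested at one week. Groups A–D are not mentioned.

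**Statistical Methods.** The plan states "60 medical students will be consented to allow for dropout" and bases power on "four groups with 10 subjects each with each subject measured 10 times, achieves 87% power". The between-subject factor named there is supine versus upright, and the comparison named is Groups A, B, C and D. Rating-scale and checklist scores go to a two-way mixed ANOVA, success or failure to Fisher's test, and time to intubation to the Mann–Whitney test. Practice versus no practice appears in none of these.

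**Research Aims.** Question 3 asks which method is retained longer, and hypothesis 2 expects the upright skill to last longer.

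**The concern.** Two randomised factors act on one outcome: teaching group, assigned on day one, and a week of practice or none, assigned afterwards. The one-week retest is the only retention measurement, so it has to serve both comparisons. The plan neither balances practice across the teaching groups nor adjusts for it.

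If practice works, a teaching group that happens to contain more practising students will look as though it retained the skill better. If practice is balanced but left out of the model, its effect goes into the error term and the orientation comparison loses precision. The practice comparison itself has no named analysis.

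There is also a gap in the numbers. Phase two provides 40 places, while up to 60 students have been randomised in Phase one and are due for the retest. The plan does not say what practice instruction a student beyond the fortieth receives.

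**Working it through.** **1. The plan's own counts.** The powered number is 4 × 10 = 40, and Phase two provides 20 + 20 = 40, so these agree. The consented number is 60, and 60 − 40 = 20. The counts meet only if the loss before Phase two allocation is 1 − 40/60 = 33.3%; check: 40/(1 − 1/3) = 60. No rate is stated. For comparison, keeping 40 needs 40/0.9 ≈ 45 students at 10% dropout and 40/0.8 = 50 at 20%.

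**2. Students without a practice arm** (60 × (1 − dropout) − 40, if 20 per arm is followed literally):

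| Dropout before Phase two | Remaining | No practice arm |
|---|---|---|
| 0% | 60 | 20 |
| 10% | 54 | 14 |
| 20% | 48 | 8 |
| 33.3% | 40 | 0 |

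**3. Chance imbalance across the four groups.** Assume 40 students, 10 in each of A–D, and 20 drawn at random to practise. There are C(40,20) = 137,846,528,820 allocations. Those in which every group has 4 to 6 practising students, using C(10,5) = 252 and C(10,4) = C(10,6) = 210, are:
- 5,5,5,5: 252⁴ = 4,032,758,016
- 4,5,5,6 in 12 orders: 12 × 252² × 210² = 33,606,316,800
- 4,4,6,6 in 6 orders: 6 × 210⁴ = 11,668,860,000

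The total is 49,307,934,816, or 35.8%. The chance that at least one group splits 7:3 or worse is therefore 64.2%. For one given group it is 27.3% (hypergeometric).

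**4. Chance imbalance between orientations.** The supine-taught half is A + C (20 students) and the upright-taught half is B + D (20). The chance that 7 or fewer, or 13 or more, of one half practise is 2 × Σ C(20,k)² for k = 0 to 7, divided by C(40,20). This is 15,553,744,284 / 137,846,528,820 = 11.3%.

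**5. What such a split does.** Let Δ be the effect of practice on the retest score. At 13:7 against 7:13, the unadjusted orientation difference is shifted by (13/20 − 7/20)Δ = 0.30Δ. Between two groups split 7:3 and 3:7, the shift is (0.7 − 0.3)Δ = 0.40Δ. The documents give no Δ. If it were 0.5, 0.7 or 1.0 SD, the 0.30Δ shift would be 0.15, 0.21 or 0.30 SD.

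**6. Illustration of using every remaining student.** The standard error of the practice contrast relative to 20 v 20 is √(40/N): 0.913, 0.861 and 0.816 for N = 48, 54 and 60. Power for an assumed difference of 0.7 SD on a single measure (two-sided 5%, noncentral t) is 58% at 20 v 20, 66% at 24 v 24, 71% at 27 v 27 and 76% at 30 v 30. For 0.5 SD, 20 v 20 gives 34% and 30 v 30 gives 48%; for 1.0 SD, 87% and 97%. The protocol's 0.7 belongs to a different test ("a difference in time to visualize the carina using a Geisser -Greenhouse Corrected F-test"), on a scale it does not define. These figures are therefore not a check of its 87%, which cannot be reproduced without the within-subject correlation and epsilon.

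**The case against.** **The 60 and the 40 are explained.** A reader might infer that the plan contradicts itself by randomising 60 and allotting 40. The documents do not support that. Statistical Methods says 60 allows for dropout and powers on 40, so 60 is naturally read as the recruitment number and 40 as the target. What remains is a missing rule: no dropout rate, and no statement whether 20 per arm is a cap or a target.

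**Selection is not shown.** A reader might also infer that the 40 would be chosen once day-one results are known. Nothing says so; Phase two says assignment is random.

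**Chance imbalance is not bias.** Averaged over randomisations, this is right. In any one trial, though, the unadjusted estimate is shifted by the split obtained, and adjustment would remove most of that shift. No adjustment is planned, so the point stands. With adjustment in place, stratifying is a further gain in efficiency rather than a necessity.

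**The 64% is the more alarming of two figures.** This is fair. It bears on a four-way comparison of A–D, which is the comparison Statistical Methods names. If question 3 is read as supine versus upright teaching, the relevant figure is 11%.

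**The ANOVA might include practice.** The sentence on the two-way mixed ANOVA does not list its factors, so practice could have been intended. The only between-subject factor and the only group comparison named concern orientation and Groups A–D.

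**Conclusion.** The concern holds for the second randomisation. Practice is assigned without reference to Groups A–D, it acts on the outcome used for retention by teaching orientation, and the planned analysis leaves it out. The chance of an uneven split is about 64% for at least one of the four groups (7:3 or worse) and about 11% between orientations (13:7 or worse). Both figures assume exactly 40 students, 10 per group, and simple random allocation of 20 to practise. The resulting distortion is proportional to the practice effect, which the documents do not give.

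The shortage of practice places is secondary. It affects at most 20 students, and only if fewer than one third are lost before Phase two. The 58% to 76% power range rests on an assumed 0.7 SD difference. It is illustrative and should not be read as a shortfall against a target, since the plan sets none for Phase two.

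One further conflict needs resolving. As far as the extracted table under Phase one can be read, its week column carries the same i/droid entry for all four groups, which does not fit a Phase two arm that is asked not to practise.

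**What to change.** 1. In Phase two, randomise all students who complete the day-one tests 1:1 to practice or no practice, stratified by Groups A–D. With 40 students (10 per group) this gives 5 and 5 in each group. With 60, and 15 per group if Phase one allocation is equal, it gives 7 or 8 per arm in each group.
2. Describe 20 per arm as the target, not a cap. It cannot be guaranteed while dropout is unknown, so state the dropout rate assumed.
3. In Statistical Methods, include teaching group and practice arm as factors in the one-week analysis, and name the practice comparison. Fisher's test and the Mann–Whitney test cannot carry a second factor, so for one-week success and time give versions stratified by the other factor, such as Cochran–Mantel–Haenszel and van Elteren.
4. Reconcile the week column of the Phase one table with the no-practice arm.

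The cost is protocol wording and a stratified list. No additional students or visits are needed, because those concerned are already due for the one-week retest.

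### The one-week retest order is fixed by group in the Phase one table but randomised in Phase two; following the table ties the upright-versus-supine retention contrast, and group B's position-specific contrasts, to test order

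*Combined protocol and SAP*

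**What the plan says.** Phase two describes a retest on the mannequin after one week and states: "Both orientations of the mannequin will be tested and the order randomly assigned".

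The Phase one group descriptions fix the day-one order (A and D supine then upright; B and C upright then supine). For the one-week session they say only that "the same medical student will then perform the intubation with the mannequin in both positions", with no order. The Phase one schedule table does give one. Its rows read:

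- "A supine supine upright i/droid upright supine", so the retest begins with upright;
- "B upright upright supine i/droid supine upright", so the retest begins with supine;
- "C supine upright supine i/droid upright supine", so the retest begins with upright;
- "D upright supine upright i/droid upright supine", so the retest begins with upright.

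The two entries after i/droid are read here as the one-week order: upright then supine for A, C and D; supine then upright for B. In the extracted text the row entries sit one cell to the left of their headers. That is an effect of extraction, and the sequence after i/droid is the same either way.

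Retention is one of the study's aims. The third research question asks: "Which method demonstrates longer skill retention". The second hypothesis includes: "The upright skill is harder to learn but is retained for longer". Statistical Methods plans a comparison of groups A to D and mentions no term for test order.

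**The concern.** Both sections appear to describe the same session. Each places a mannequin retest at one week, and the table's i/droid entry fits the smartphone practice of Phase two. An examiner cannot draw the order at random and also take it from the table, and no section says which has priority.

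The choice matters because the one-week session supplies the retention data. A student's second test of the session may be better through warm-up or transfer, or worse through fatigue. Under the table, 3 of 4 groups (30 of the 40 students in the power statement) meet upright first. Any order effect then enters the comparison of upright with supine retention, and it also enters within-position comparisons of the one group with the opposite order, B.

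**Working it through.** **Plan's own figure.** The plan gives no figure for an order effect. Its 87% power concerns repeated timings and does not enter this check.

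**Inputs.** Teaching position and day-one order come from the Phase one group descriptions, one-week order from the Phase one table, and 10 students in each of four groups from Statistical Methods. Assumption: the second-tested position shifts by g (either sign), additively, equally in both directions and equally at both sessions.

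**Step 1: shift by group.** Each cell pair is (upright, supine); U-S is upright minus supine.

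| Group | Taught | Day one | One week | U-S day one | U-S one week | U-S change | Upright change |
|---|---|---|---|---|---|---|---|
| A | supine | (g, 0) | (0, g) | +g | -g | -2g | -g |
| B | upright | (0, g) | (g, 0) | -g | +g | +2g | +g |
| C | supine | (0, g) | (0, g) | -g | -g | 0 | 0 |
| D | upright | (g, 0) | (0, g) | +g | -g | -2g | -g |

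The change in supine has the opposite sign to the change in upright.

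**Step 2: upright minus supine.**
- One week, pooled: (-1 + 1 - 1 - 1)g/4 = -0.5g. Supine-taught (A, C): -1.0g. Upright-taught (B, D): 0.
- Day one, pooled: (1 - 1 - 1 + 1)g/4 = 0, and 0 within each teaching pair.
- Change from day one therefore shifts by the same amounts as one week: -0.5g, -1.0g and 0.

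**Step 3: group contrasts within one position, at one week.** In upright, B carries g and A, C and D carry 0; in supine the pattern reverses. B against A, C or D shifts by 1.0g in size. A, C and D against each other shift by 0. Upright-taught against supine-taught: (g + 0)/2 - (0 + 0)/2 = 0.5g, with opposite sign in supine.

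**Step 4: change from day one within one position.** From the last column: B against A or D, 2.0g; B against C, 1.0g; C against A or D, 1.0g; A against D, 0; teaching, (g - g)/2 - (-g + 0)/2 = 0.5g.

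**Step 5: average over both positions.** Each group carries g/2 at one week, so group contrasts shift by 0, but only because the shift was taken as equal in both directions. Let it be gU when upright is second and gS when supine is second. B's average is gU/2 and that of A, C and D is gS/2. B against any other group then carries (gU - gS)/2. The teaching contrast carries (gU/2 + gS/2)/2 - gS/2 = (gU - gS)/4. With assumed gU = 0.5 and gS = 1, these are -0.25 and -0.125.

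**Step 6: the same quantities under random retest order.** Every group expects 0.5g in each position at one week, so one-week group contrasts expect 0. Upright minus supine expects (gU - gS)/2, which is 0 only if the shifts are equal. Day-one order is still fixed, so the change in upright is -0.5g for A and D and +0.5g for B and C: B or C against A or D still shifts by 1.0g.

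**Step 7: illustration only.** Assume a group-by-position mixed ANOVA at one week, 10 per group, 5% level, no true effect, and g in SDs of the within-student difference. Noncentrality for position is 40 × (0.5g)² = 10g². For group-by-position it is 10 × (0.25 + 2.25 + 0.25 + 0.25)g² = 30g².

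| Assumed g | Position F(1,36) | Group-by-position F(3,36) |
|---|---|---|
| 0.2 | 9% | 12% |
| 0.5 | 34% | 57% |
| 1.0 | 87% | over 99% |

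**Step 8: if row C is a slip.** A, B and D reverse their day-one order and only C repeats it. With C reversed, the one-week U-S shifts are -g, +g, +g, -g. The pooled and by-teaching shifts become 0, but group-by-position noncentrality rises to 40g² (15%, 71% and over 99%).

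**The case against.** **Groups are randomised, so an order set by group is itself randomly assigned.** This would remove the literal conflict. It would not remove the consequence: order would still be fully tied to group and split 3:1, or 2:2 if row C is a slip.

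**The evidence is one damaged table, possibly with a slip in row C.** The slip is possible and would bring the pooled position shift to 0. Order would still be fixed by group and still disagree with Phase two.

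**The size is unknown and the tests are assumed.** This stands. The documents give neither size nor sign of an order effect. Statistical Methods names repetitions, not position, as the within factor and does not specify a one-week group-by-position model. The percentages above are illustrations. The multiples of g follow from the documents' test orders, given the stated assumptions about the shift.

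A reader might infer three further things that the documents do not support:

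- That every position-specific group contrast at one week is affected. It is not: A, C and D share one order in the table, so only contrasts containing B are.
- That comparisons averaged over both positions are safe in any case. They are safe only if the shift is equal in both directions. The second research question asks whether skill transfers from supine to upright, so equality cannot be presumed.
- That following Phase two removes all order bias. It does so for one-week group contrasts, but not for position-specific change from day one, because day-one order remains fixed by group.

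**Conclusion.** The contradiction is real and must be reconciled. If the table governs, the one-week upright-minus-supine contrast and its change from day one shift by -0.5g pooled and -1.0g in the supine-taught groups, with none in the upright-taught groups. Within one position at one week, B's contrasts with each other group shift by 1.0g and the teaching contrast by 0.5g. On position-specific change, B against A or D shifts by 2.0g, and B against C and C against A or D by 1.0g.

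These multiples assume an additive shift, equal in both directions; those on position-specific change also assume the same shift at both sessions. With unequal shifts, averaged group comparisons involving B are affected as well. A practice versus no-practice comparison is not biased by order if practice is allocated independently of groups A to D.

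This does not show that the retention result will be wrong: the table may not be the rule used, and g may be small. It is a point that should be corrected before testing starts, since the remedy is cheap.

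**What to change.** 1. Remove the fixed one-week order from the Phase one table and apply the random order of Phase two, balanced 1:1 within each of groups A to D.
2. Include retest order as a term in the one-week position analyses. Simple randomisation already frees one-week group contrasts from order in expectation; balance and the term add precision. Under simple randomisation without the term, the variance of upright minus supine is multiplied by 1 + g², that is 1.04, 1.25 or 2.00 at an assumed g of 0.2, 0.5 or 1.0 SD.
3. An additive order term does not repair unequal shifts, so also report upright minus supine separately by order, or from first-tested positions only. The latter compares different students and is less precise.
4. State that position-specific change from day one for B or C against A or D still carries 1.0g from the day-one order. Base such comparisons on one-week scores, or on groups that share a day-one order (A with D, B with C).
5. If a fixed one-week schedule is kept, balance order within each teaching position. Reversing row C or row A gives 0 pooled and 0 by teaching. Reversing row D gives 0 pooled but leaves -1.0g in the supine-taught and +1.0g in the upright-taught groups. State that group-by-position and position-specific contrasts between individual groups remain confounded with order.

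Cost: one table correction, one balanced order list and one model term; no extra students or visits.
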